## Phase 2 Protocol

This study is designed to understand how coaching versus standard education impacts pediatric providers' recommendation of the etonogestrel contraceptive implant to adolescent girls considering contraception.

A cohort of 100 providers will be recruited. A pediatric provider is defined for this study as an MD, DO, PA, or APRN who is fully licensed in the state of Florida and graduated with the degree. To participate this individual must have a practice that provides care to female patients under the age of 18 in a pediatrics, family medicine, internal medicine or obstetrics/ gynecology practice that refers patients for or provides contraception in their practice. The provider must devote at least 50% of their practice to primary care or reproductive health. A provider can also see patients 18 years of age and older. More than one provider in a practice may participate. A minimum of 30% APRN or PA providers will be recruited.

By participating in the study, the pediatric provider is agreeing to participate in a 6-month long educational experience for the provider.

The cohort will be randomized into two groups. The control group is comprised of providers who will receive an educational activity and tip sheet. The experimental group is comprised of providers who will receive an educational activity and tip sheet plus an at-will coaching resource. Both groups will receive the educational activity together in a virtual platform as well as the same written tip sheet at the end of the educational activity. Both groups will be administered the same pre-test and post-test at beginning and end of educational activity via a redcap survey.

The educational activity was created based on Phase 1 of this study which identified the most common barriers in providing etonogestrel contraceptive implant to adolescents who reside in North & Central Florida and the areas of highest knowledge deficit. Topics included in this program are:

- Best practices in contraception counseling for teens
- Adolescent attitudes towards the contraceptive implant
- Parental attitudes towards the contraceptive implant
- Cost and access to contraception
- Physical characteristics of the contraceptive implant
- Indications and contraindications to receiving the contraceptive implant
- Understanding the implant placement procedure
- Most common side effects of the contraceptive implant
- Menstrual bleeding profile following placement of the implant

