Each participant will receive an educational packet that will include: the slides and a troubleshooting tip sheet mailed to them prior to the date of educational event. The trouble shooting tip sheet will have the key take away points from the educational program. Participants who have consented to the study will additionally receive a contraception discussion tracking form, that will be color coded and labelled for each month of the study to indicate whether the participant has been randomized to the control group or the experimental group. As well as instructions on how to enroll in the MOC program. The referral form will have an email address at the bottom that the participant should use to return in their contraception discussion tracking forms. The tracking form will have the participant for each day record the number of patients under 18 who they discussed contraception with, the number who chose the implant, the number who chose another reliable contraceptive method, and number who chose no option. There will also be a place for the provider to record any reflections or questions they have. Each week participants will receive an email reminding them to enter the information from the tracking form into the MOC portal. They will receive a survey on months 2,4, and 6 via red cap asking them about practice changes and challenges experienced while trying to implement increased counseling. For participants in the experimental group their tip sheet has an email address they can use to access coaching. Additionally, this email will be included in all communication reminding them to enter their tracking form information into the MOC portal. Coaching is at will and is initiated by sending an email with a non-emergent question that will be answered within two business days. If the principal investigator is on vacation or unavailable, then the participant will be notified that coaching is not available and that they should proceed as they typically would without coaching. Questions will be categorized as to whether they are related to: indication, procedure question, post-placement bruising, post-placement breakthrough bleeding, post-placement weight gain, other post-placement side effect. These categories were selected based on data from Phase 1 questionnaire that showed these are areas that providers are less knowledgeable in addressing.

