To assure the principal investigator remains blind to which participants are in the control vs experimental group several precautions will be taken. The principal investigator will not be involved in the check-in process of the educational program. Additionally, during data collection the tracking information will be routed to the study coordinator. Additionally, any questions initiated through coaching will route to an email that only the study coordinator has access to. The study coordinator will route the email to the PI without any identifying information. The investigator will return the email to the study coordinator with an answer, who will return the answer to the participant. This ensures the investigator will remain blind to which group the participants are in.

Over the course of 6 months the number of contraceptive discussions, number of patients who chose the implant, another reliable method, and no method will be tabulated for the experimental and control groups. Additionally individual providers trends over time for each of these variables will be analyzed for each group.

At the conclusion of the data collection period, five participants from each group will be selected at random to participate in a focus group. This focus group will last 1 hour. It will be audio recorded and analyzed to elicit narrative on barriers to counseling, referring, and managing patients with etonogestrel implant. Focus group participants will be compensated with a \$100 gift card for their time.

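### Group totals and provider trends are counts with no denominator, and the form as described records no clinic days, so unequal recording between arms would look like unequal counselling

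*Protocol*

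**What the plan says.** The protocol has one section, Phase 2 Protocol. Three parts of it matter here.

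- **Design.** "A cohort of 100 providers will be recruited" and "The cohort will be randomized into two groups". The allocation ratio is not given.
- **Data collection (tracking-form paragraph).** "The tracking form will have the participant for each day record the number of patients under 18 who they discussed contraception with", and then "the number who chose the implant, the number who chose another reliable contraceptive method, and number who chose no option". There is also space for reflections or questions. No field for days in clinic is described. The forms are coloured by arm and labelled by month, and are returned by email. For both arms, "Each week participants will receive an email reminding them to enter the information from the tracking form into the MOC portal". In the experimental arm these reminders also carry the coaching address.
- **Summary (tabulation paragraph).** The list of quantities opens with "Over the course of 6 months the number of contraceptive discussions, number of patients who chose the implant" and goes on to patients choosing a different reliable method or none. All of these "will be tabulated for the experimental and control groups". In addition, "individual providers trends over time for each of these variables will be analyzed for each group".

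Neither the tabulation nor the trends are stated per day, per patient seen or per discussion.

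**The concern.** A count summed over six months is the product of how often a provider counsels and how much of that counselling is written down. The protocol wants the first and, as worded, measures the product. A clinic day left blank adds nothing to a total, just as a day with no discussions does.

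Randomisation balances practice volume on average. It does not protect against this problem, because recording happens after randomisation and is done by providers who know their arm. The prompt to record also differs: the experimental arm is reminded of the coaching offer each time, and providers who use coaching exchange messages through the coordinator who also receives the tracking data. Either could keep one arm more engaged with the form. An arm that records more would then show more discussions and more implant choices with no change in practice.

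The individual trends have a related weakness. A provider who counsels at a constant rate but records less each month will appear to counsel less.

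**Working it through.** The protocol states no completion rate, discussion rate, effect size or significance level, so there is no figure of its own to reproduce. Every completion rate below is an assumption.

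**1. Group totals.** Expected total = providers × clinic days × completion × discussions per day. With equal numbers of providers, clinic days and true daily rates, everything cancels except completion:

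ratio of totals = completion (experimental) ÷ completion (control)

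For scale, the totals assume 50 providers per arm (100 split equally), 126 clinic days each and 1 discussion per day, so 50 × 126 × 1 = 6300 discussions per arm at full recording.

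| Assumed completion, experimental vs control | Expected totals | Ratio |
|---|---|---|
| 80% vs 80% | 5040 vs 5040 | 1.00 |
| 80% vs 76% | 5040 vs 4788 | 1.05 |
| 90% vs 80% | 5670 vs 5040 | 1.125 |
| 80% vs 70% | 5040 vs 4410 | 1.14 |
| 90% vs 75% | 5670 vs 4725 | 1.20 |
| 80% vs 60% | 5040 vs 3780 | 1.33 |
| 90% vs 60% | 5670 vs 3780 | 1.50 |

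The ratios do not depend on the 126 days or the 1 per day. Reversing the arms inverts them.

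**2. Could this be mistaken for an effect?** A simulation with no true difference used the same scale, gamma variation between providers (shape 2 or 4), beta-distributed completion (precision 8), a Welch t-test on provider values at two-sided 0.05, and 4000 runs per setting. The test is an assumption too, since the protocol names none.

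| Completion | False positives, totals (shape 2 / 4) | False positives, per recorded day (shape 2 / 4) |
|---|---|---|
| 80% vs 80% | 5.1% / 4.7% | 5.6% / 4.5% |
| 80% vs 70% | 12.9% / 22.1% | 5.1% / 5.2% |
| 80% vs 60% | 46.0% / 70.3% | 4.6% / 5.3% |
| 90% vs 60% | 74.5% / 94.1% | 5.3% / 5.0% |

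The implant share among recorded discussions differed between arms by 0.000 in every setting. The results for the rate and the share hold because the simulation makes unrecorded days resemble recorded ones.

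**3. Individual trends.** With constant practice and completion falling from an assumed 95% in month 1 to 60% in month 6, the apparent change is 1 − 0.60/0.95 = 0.37, a false decline of 37%. If both arms fall alike, the month-6 ratio is 0.60/0.60 = 1.00 and the arm comparison is intact. If one arm stays at 95% while the other falls to 60%, the month-6 ratio is 0.95/0.60 = 1.58.

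**4. What can be recovered from the form as described?**

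- A month never returned: yes, from the month labels.
- A blank day against a zero day: yes, where providers write the zero.
- A day off against an unrecorded clinic day, when both are blank: no.
- Clinic days worked: no.

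**The case against.** The protocol does not say that totals are raw sums or that a blank counts as zero. It says that numbers are tabulated and trends analysed. Denominators and missing-day rules are often left to a statistical analysis plan, which is not at hand. A provider told to record a number for each day may well write zeros, and portal entries may give a second record. Both arms have the same form fields and the same weekly reminder, and coaching is at will and may never be used. The form itself is not reproduced; one sentence lists its fields. The share choosing the implant can be formed from the same data, and it suits a study about recommending the implant.

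Most of this stands as a limit. A reader might infer that the protocol fixes a biased comparison that no analysis could repair. The documents do not support that: they give no evidence that completion will differ or in which direction, and step 4 shows that part of the gap can be closed. A reader might also take the 37% decline as an arm bias, but it is a within-provider artefact unless the fall differs by arm.

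What the objection does not remove is narrower. The summary is worded as counts, and no later plan can supply clinic days that the described form does not collect. The share helps with choices but offers nothing for the number of discussions, which is itself a listed outcome.

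The rate is not immune either. If providers mainly fill in the form on days with a discussion, a rate per recorded day is too high while the total is nearly right.

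**Conclusion.** The point holds in conditional form. As worded, the group totals carry any difference in recording completion one for one: 12.5% for an assumed 90% against 80%, 5% for 80% against 76%, and nothing when completion is equal. A difference is plausible because providers know their arm and the reminders differ, but it is not shown and its direction is uncertain. The calculation assumes equal provider numbers, clinic days and true rates, and reads the tabulation plainly as counts without a denominator. The part that cannot be mended afterwards is limited to clinic days worked and unmarked blank days within returned forms. The change should be made before forms are issued, as an inexpensive improvement to the measurement rather than as the repair of a demonstrated bias.

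**What to change.** - **Form.** Add a daily tick for in clinic or not in clinic, and require a written 0 on clinic days without a discussion.
- **Summary.** Tabulate and trend each count per recorded clinic day, alongside the totals. Treat blank clinic days as missing.
- **Completion.** Show recorded and total clinic days by arm and month next to the counts.
- **Companion.** Report the implant share among recorded discussions, which is less sensitive to completion.

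The cost is one tick per day, a 0 where the cell might have been left empty, and a few extra table columns. The rate and the share both still assume that recorded days resemble unrecorded ones. That is why the totals stay in the table and completion by arm stands beside them: if completion is similar in the two arms the reader can rely on any of the summaries, and if it is not the reader can see how far the totals might be affected.

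### The aim is a randomised comparison of coaching with standard education, but the tracking-form analyses as stated are counts by arm and trends within each group, with no between-arm comparison stated

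*Protocol*

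**What the plan says.** The protocol has a single section, Phase 2 Protocol. Four of its statements bear on this point.

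- **Aim.** "This study is designed to understand how coaching versus standard education impacts pediatric providers' recommendation of the etonogestrel contraceptive implant" to adolescent girls considering contraception. This is a comparison of two strategies.
- **Design.** "A cohort of 100 providers will be recruited", and "The cohort will be randomized into two groups". The provider is the randomised unit. No allocation ratio is given.
- **Data.** The tracking form has each provider "for each day record the number of patients under 18 who they discussed contraception with, the number who chose the implant", with further entries for another reliable method and for no option. Numerator and denominator are therefore collected by provider and by day.
- **Analysis.** Over 6 months, "the number of contraceptive discussions, number of patients who chose the implant, another reliable method, and no method will be tabulated" for the two groups; the sentence closes with the words "no method will be tabulated for the experimental and control groups". In addition, "individual providers trends over time for each of these variables will be analyzed for each group".

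The last item holds the only analyses stated for the tracking-form counts. It names no contrast between the groups, no rate or proportion, and no interval or test.

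**The concern.** A protocol may leave models, covariates and standard errors to an SAP. This one does state how its main data will be analysed, and what it states does not match its aim in two respects.

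- **Totals.** A table of counts by arm is descriptive. The number of implant choices in an arm depends on how many contraceptive discussions its providers happen to have, as well as on what patients choose in those discussions. Eligible practices include pediatrics, family medicine, internal medicine and obstetrics/gynecology, so there is no reason to expect equal volumes. Since discussions are tabulated too, a crude implant share per arm can be derived. The totals alone, however, do not show how far providers differ from one another.
- **Trends.** If trends are read arm by arm, a rise under coaching and no clear rise under education does not show that the two trends differ. The effect of coaching is the difference between arms, and that has to be estimated directly.

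At stake is whether the report can present an estimate of the coaching effect, with its uncertainty, as the randomisation intended. An SAP that followed these two sentences literally would inherit the mismatch.

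**Working it through.** **No figure to reproduce.** The 100 providers come without alpha, power, effect size or variance, so the number cannot be recomputed. What follows only illustrates why the comparison and its unit matter.

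**Inputs.** From the protocol: 100 providers, two groups, 6 months, counts by provider. Assumed, because the protocol gives none of them: 50 providers per arm (n = 50), implant share p = 20%, no coaching effect, m discussions per provider, intracluster correlation ICC, and a coefficient of variation CV of provider volume from 0 to 1.0.

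**Step 1: what the arm totals alone could support.** The binomial 95% half-width for the difference in shares is 1.96 × √(2p(1−p)/(nm)).
- m = 10: 1.96 × √(0.32/500) = 5.0 points
- m = 50: 1.96 × √(0.32/2500) = 2.2 points
- m = 100: 1.96 × √(0.32/5000) = 1.6 points

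**Step 2: what variation between providers adds.** The variance is inflated by DE = 1 + ((1 + CV²)m − 1) × ICC, and the half-width by √DE.

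| m, ICC | CV | DE | √DE | Half-width, points |
|---|---|---|---|---|
| 10, 0.01 | 0 | 1.09 | 1.04 | 5.2 |
| 10, 0.01 | 1.0 | 1.19 | 1.09 | 5.4 |
| 50, 0.02 | 0 | 1.98 | 1.41 | 3.1 |
| 50, 0.02 | 1.0 | 2.98 | 1.73 | 3.8 |
| 100, 0.05 | 0 | 5.95 | 2.44 | 3.8 |
| 100, 0.05 | 1.0 | 10.95 | 3.31 | 5.2 |

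**Step 3: check by simulation.** Beta-binomial implant choice was simulated with 20,000 runs per cell.
- The chance ranges agreed with the table: about ±5.2 to 5.5, ±3.1 to 3.8 and ±3.8 to 5.2 points for the three settings.
- Provider-based intervals were wider than binomial ones by factors of 1.06 to 1.08, 1.4 to 1.7 and 2.5 to 3.2.
- The binomial interval covered the true difference 93–94%, 75–84% and 46–57% of the time.
- The provider-based comparison had a type I error of 5.0–6.2% over all cells.

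**Step 4: why totals are a poor basis for comparison.** Take m = 50, ICC 0.02, CV 0.8, so DE = 1 + (1.64 × 50 − 1) × 0.02 = 2.62.
- Ratio of implant shares: log variance 2 × (0.8/0.2)/2500 × 2.62 = 0.0084. The 95% chance range is exp(±1.96 × √0.0084), or 0.84 to 1.20.
- Ratio of implant totals: volume adds 2 × 0.64/50 = 0.0256, giving 0.0340. The range is exp(±1.96 × √0.0340), or 0.70 to 1.44. Simulation gave 0.69 to 1.45.

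With no effect of coaching at all, the ratio of totals can thus stray more than twice as far from 1 as the ratio of shares. Using the denominator removes the part due to volume; the variation between providers remains.

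**The case against.** The strongest reply is that this is SAP content. Unit of analysis, clustered variance, effect measure and interval are often left to that document, which may exist. The aim is comparative, both groups are tabulated on the same variables, and analysing trends for each group can be read as doing so for both groups in order to compare them. Much of this stands: the text does not exclude a comparison, and the absence of a named model or test is no error. The mismatch between the aim and the analyses actually written down remains.

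A reader might go further and infer that the plan can yield only a crude difference with no provider-based uncertainty, so that the trial could not tell a coaching effect from chance. The protocol does not support that. Its trend sentence analyses individual providers in both arms, which could carry the variation between providers, and the provider-level data are collected. Nor does the protocol prescribe a pooled binomial interval, so the poor coverage above is no property of its plan; it only shows what arm totals leave out.

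It is also fair that every input to the illustration is assumed, that the three settings raise volume and ICC together, and that the mildest one shows almost no gap. Finally, the protocol names none of its counts as primary, so choosing implant choices per discussion is a proposal. It is the measure closest to the stated aim that the form supports.

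**Conclusion.** The point holds in limited form. The aim and the randomisation call for a between-arm comparison at provider level. The analyses stated for the tracking-form data are raw counts by arm and provider trends for each group, and neither sentence says that the arms are compared. Provider-level summaries are foreseen; their use for the comparison is not stated.

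The practical size is unknown. On the assumptions listed, the widening relative to pooled counts runs from negligible (a factor of 1.06 to 1.08 at 10 discussions and ICC 0.01) to 2.5 to 3.2 at 100 discussions and ICC 0.05. The dependence of raw totals on provider volume needs no ICC; it needs only unequal volumes. This should be changed, with medium confidence: the wording is clear, but an SAP not shown here may already settle it.

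**What to change.** Add to the analysis paragraph of Phase 2 Protocol one or two sentences to this effect: the randomised groups will be compared on implant choices per contraceptive discussion over the 6 months, with the provider as the unit of analysis (a provider-level summary, or a model that accounts for clustering by provider), reported as one between-arm difference or ratio with a 95% CI. If trends are of interest, state that provider slopes will be compared between arms.

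Keep the tabulations and the per-group trends as description. Show the discussion counts beside the implant share, because the share conditions on discussions and coaching may itself change how many take place. Leave further model details to the SAP.

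The cost is a little more analysis work and intervals wider than pooled counts would give, by the factors above. No new data are needed, since the tracking form already holds both counts for each provider.
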